#### 10.5.5.1 25-35 Minute Pacing

Subjects in the MODULAR ATP Clinical Study are not expected to need a high level of pacing. Therefore, participating subjects will have a 30±5-minute pacing period prior to finalizing the 1-month follow-up.

After the Holter is applied, and prior to the end of the visit,  $30\pm5$  minutes of pacing will be collected. Determine the subject's intrinsic rate, and program LRL to approximately 5-10ppm above the intrinsic rate, with EMPOWER in VVI. Investigator discretion and/or the subject's tolerance of pacing should be considered when choosing the LRL or adjusting it after pacing has started. The subject should be instructed to sit calmly for  $30\pm5$  minutes. Document the time of programming the higher LRL, and time of programming the LRL back to the intended programmed value. The investigator has the discretion to stop the pacing early due to subject condition; the rationale for early stopping will be collected.

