## 10.3.2.5 S-ICD Programming

S-ICD programming is left to physician discretion until mCRM Coordinated System testing is completed, as described in **Section 10.3.4**.

MODULAR ATP

Page 50 of 148

**Note**: Until the Paced Morphology Sensing Test (PMST) has been completed (and passed), the EMPOWER LRL should be programmed to <1/3 of the lowest S-ICD detection limit per the mCRM PTM. Refer to **Section 10.3.4.6**.

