10.3.4.6 Paced Morphology Sensing Test (PMST)

PMST is important to complete to determine appropriate S-ICD settings to avoid oversensing for subjects receiving pacing from the EMPOWER PG. A sensing vector that appropriately senses both the paced and intrinsic rhythms avoids S-ICD oversensing of the evoked response and the possibility of delivering inappropriate shock therapy

• Program the S-ICD to Therapy Off.

Set the subject's EMPOWER PG:

- mode to VVI,
- pacing output to ensure capture, and
- LRL to 10-20 ppm above their intrinsic rate (with a maximum of 120 ppm) to promote pacing.

Use the 'Capture All Sense Vectors' feature of the S-ICD programmer to collect and retain S-ECG snapshots in the supine posture for each S-ICD sensing vector.

**Note:** a deviation shall not be assessed for subjects who cannot tolerate this testing due to high-rate pacing.

Document any oversensing, e.g., double counting, on the associated Form in EDC, and collect the "Captured S-ECG Reports" generated from the Manual Setup feature on the S-ICD programmer.

If there is an S-ICD vector that demonstrates appropriate sensing for both intrinsic and paced rhythms, this vector should be used, which will minimize the risk of oversensing and inappropriate shocks. If there is not an S-ICD vector that demonstrates appropriate sensing for both intrinsic and paced rhythms, a vector that demonstrates appropriate

```
Page 55 of 148
```

sensing of intrinsic rhythms should be used, and the EMPOWER PG's LRL should be programmed to <1/3 of the lowest programmed S-ICD tachy detection zone.

When the PMST is complete, program the S-ICD to Therapy On.

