# 10.5.4 mCRM Coordinated System Programming

Recommended programming parameters for the EMPOWER PG and S-ICD are included in **Sections 10.4.4.1** and **10.4.4.2**, respectively.

Print out a copy of the final "Combined Follow-up Report" and a copy of the "S-ICD Summary Report". Once all study activities are completed at the end of the visit, reset the EMPOWER PG brady counters/ histograms and tachy counters.

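### The 1 Month Holter pacing step (10.5.5.1) is not tied to the PMST result, so a participant without a passing vector could be paced temporarily above the one-third rate limit

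*Protocol*

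**What the plan says.** **The Holter step.** Protocol 10.5.5.1 gives each Holter participant 30±5 minutes of seated pacing before the 1 Month Visit ends: "Determine the subject's intrinsic rate, and program LRL to approximately 5-10ppm above the intrinsic rate, with EMPOWER in VVI". The investigator may use discretion and the subject's tolerance in choosing or adjusting the rate, and may stop early. The site records when the LRL is raised and when it is restored. The PMST, the sensing vector and S-ICD therapy status are not mentioned.

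**The rate safeguard.** Section 10.3.4.6 covers the subject in whom no vector senses both rhythms properly: "LRL should be programmed to <1/3 of the lowest programmed S-ICD tachy detection zone". Before a PMST has been passed, 10.3.2.5 says "the EMPOWER LRL should be programmed to <1/3 of the lowest S-ICD detection limit", citing the mCRM Physician's Technical Manual (PTM).

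**Programming at the same visit.** Section 10.5.4 says "Recommended programming parameters for the EMPOWER PG and S-ICD are included in" 10.4.4.1 and 10.4.4.2. Table 10-8 in 10.4.4.1 recommends an LRL below one third of the conditional shock zone's lower bound and gives no Holter exception.

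**How the PMST handles similar pacing.** It sets the "LRL to 10-20 ppm above their intrinsic rate (with a maximum of 120 ppm) to promote pacing", but first instructs: "Program the S-ICD to Therapy Off". Table 10-1 requires the PMST at System Testing and Pre-Discharge and does not schedule it at 1 Month. A subject may lack a result without a deviation: "a deviation shall not be assessed for subjects who cannot tolerate this testing due to high-rate pacing".

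**The concern.** The PMST exists because the S-ICD may count a paced beat more than once, reach its detection zone and deliver an inappropriate shock. The protocol guards against this in several places. It limits the LRL until a vector has passed, makes rate-responsive modes conditional on sensing of paced beats (10.4.4.1), and turns therapy off while the PMST itself paces above intrinsic. Section 10.5.5.1 raises the pacing rate for about half an hour and states neither a sensing condition nor a therapy-off instruction.

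The pacing is imposed by the study on subjects whom 10.5.5.1 itself expects to need little pacing. A subject who failed or could not tolerate the PMST stays in the study, and nothing in 10.5.5 excludes that subject from the Holter substudy. In such a participant, following 10.5.5.1 to the letter could recreate the situation that 10.3.4.6 is written to avoid. What is at stake is the safety of a few participants at one visit.

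**Working it through.** **Inputs**

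- Zone lower bound Z = 180 bpm: the example in Table 10-8, and the lower end of the recommended primary-prevention zone in Table 10-9.
- Holter increment d = 5 to 10 ppm (10.5.5.1).
- LRL limit: below Z/3 (10.3.4.6, 10.3.2.5, Table 10-8).
- Assumption: every paced beat is counted n times, so counted rate = n × paced rate.
- Assumption: Z of 170 and 200 bpm as a range, because Table 10-10 leaves secondary-prevention zones to the physician.
- Intrinsic rates are not given in the documents, so results are stated as crossing points.

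**Step 1: the plan's own figure.** Z/3 = 180/3 = 60. This matches the Table 10-8 example of an LRL below 60.

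**Step 2: where Holter pacing reaches the limit.** Paced rate = intrinsic + d, so the limit is reached at intrinsic = Z/3 − d. For Z = 180 this is 60 − 10 = 50 (at +10) and 60 − 5 = 55 (at +5). In oversensing terms this is the triple-counting point: 3 × 60 = 180.

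**Step 3: where double counting reaches the zone.** Double counting is the example the protocol names: "Document any oversensing, e.g., double counting, on the associated Form in EDC". It needs a paced rate of Z/2 = 90, so an intrinsic rate of 90 − 10 = 80 (at +10) to 90 − 5 = 85 (at +5).

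**Step 4: check at intermediate rates.** Intrinsic 60 to 70 gives a paced rate of 65 (60 + 5) to 80 (70 + 10). Double counted, that is 130 to 160, below 180. Triple counted, it is 195 to 240, inside the zone.

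| Zone Z (bpm) | Z/3 | Intrinsic rate at which LRL limit is reached | Z/2 | Intrinsic rate at which double counting reaches zone |
|---|---|---|---|---|
| 170 (assumed) | 56.7 | 46.7–51.7 | 85 | 75–80 |
| 180 (protocol) | 60 | 50–55 | 90 | 80–85 |
| 200 (assumed) | 66.7 | 56.7–61.7 | 100 | 90–95 |

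**Step 5: who is affected.**

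- *Programmed vector passed the PMST.* Sections 10.3.2.5 and 10.3.4.6 no longer limit the LRL. The PMST used 10–20 ppm above intrinsic, a larger increment than the Holter step's 5–10. Only the Table 10-8 recommendation is left, temporarily.
- *No vector passed.* The 10.3.4.6 limit applies, and 10.5.5.1 does not refer to it.
- *PMST not tolerated.* There is no pass, so the 10.3.2.5 limit applies, and the site has no sensing result to consult.

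The size of the last two groups is not given and cannot be derived.

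**Step 6: room in the Holter substudy.** Section 10.5.5.2 needs 25 usable recordings from about 50 subjects, leaving 50 − 25 = 25 to spare. It defines usable by hours recorded (at least 16), so omitting forced pacing does not itself lose a dataset. This margin therefore does not measure the loss of forced-pacing data.

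**The case against.** A reader might infer that 10.5.5.1 contradicts the one-third rule outright and that a site cannot follow both. The documents do not support that reading:

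- The limits in 10.3.4.6 and Table 10-8 can be read as governing how the device is left programmed. The Holter step is temporary and ends with the intended LRL restored, which can comply. The protocol also accepts brief pacing above the limit in the PMST.
- Section 10.5.5.1 gives discretion over the LRL itself. Section 10.5.5 gives medical discretion over who takes part, and passing over a subject is not a deviation. A site can omit a subject without a passing vector and break no instruction.
- The site normally holds the PMST result, oversensing is recorded in EDC, and a passing vector should be the one used. Vector changes at 1 Month are documented (10.5.2.1).
- Subjects excused the PMST are those who cannot tolerate high-rate pacing, and 10.5.5.1 tells the investigator to consider tolerance of pacing.
- The PTM and separate Holter instructions (mentioned as possible in 13.4) may contain the check. Section 16.2 requires the device to be used according to its instructions as well as the protocol.

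Most of this stands, and it limits both the reach and the likelihood of the problem. What remains is that the discretion is general or concerns tolerance and the subject's condition. Nothing in 10.5.5 or 10.5.5.1 points the investigator to S-ICD sensing, and pacing can be well tolerated yet oversensed. The PMST precedent also does not carry over fully, because that test turns therapy off first.

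**Conclusion.** The point holds as a low-probability subject-safety inconsistency, and a cheap one to remove. For a Holter participant whose programmed vector has not passed the PMST, literal adherence to 10.5.5.1 departs temporarily from the LRL safeguard in 10.3.4.6 and 10.3.2.5, with therapy status unstated.

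A reader might also take an intrinsic rate of 50 to 55 as the point where shocks become likely. It is not. It is where the LRL limit is reached, and reaching the zone there would need every paced beat to be counted three times. Double counting needs 80 to 85 with a 180 bpm zone. The exposure is short, takes place during the visit, and can be adjusted or stopped.

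The conclusion rests on the uniform-counting assumption and on the supplied documents alone. If the PTM or Holter instructions already require a passing vector, only a cross-reference is missing. No endpoint test, sample size or alpha is affected.

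**What to change.** Add one sentence to 10.5.5.1: carry out the elevated-LRL pacing period only if the S-ICD vector now programmed sensed both paced and intrinsic beats appropriately on the PMST; otherwise omit the pacing period, though the Holter may still be worn.

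This uses a result already required by Pre-Discharge and adds no new test. The cost is that subjects without a passing vector contribute no forced-pacing data, although they can still supply a usable 16-hour recording. If those data are wanted, the alternative is to turn S-ICD therapy off for the period, as the PMST does, and to say so in the section. That would leave the subject without device shock therapy for 25 to 35 minutes, so the simple condition is preferable unless the sponsor has a reason to need the data.

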#### 10.5.5.2 16 to 24 Hour Holter Monitoring

Complete data recording consisting of at least 16 hours of usable data from a minimum of 25 subjects are required, and it is expected that an enrollment of 50 subjects will be sufficient to provide the minimum number of datasets required. Once BSC determines that the requirement of 25 usable datasets is met, Holter substudy sites will be notified that the Holter monitoring is no longer needed for any additional subjects and the Holter monitoring part of the clinical study will be completed.

Page 66 of 148

# 10.5.6 1 Month Visit Source Documentation Requirements

The 1 Month Visit data and source documentation requirements are listed in **Table 10-12**.

Data Collection	Retention of Original Source Documentation
EMPOWER Programmer Reports:	
- Initial EMPOWER Combined Follow-up Report	

 
EMPOWER Real-Time Log Report (to document loss of capture)
 
	Study site
- Final EMPOWER Combined Follow-up Report	
S-ICD Programmer Reports:	
- S-ICD Summary Report from the end of the visit	Study site; upload copy to BSC via study EDC system
- Full S-ECG Report(s) Treated, if applicable	
- Full S-ECG Report(s) Untreated, if applicable 	
- Communication (Threshold) Test S-ECG Reports	Study site
- Order of postures tested documented on TSF	
Holter Substudy:	

 
- (Clock) Time of programming to LRL +5-10ppm above intrinsic
 
	
- (Clock) Time of programming to intended LRL	Study site

 
Information regarding the Holter monitor distribution, and return
 
	
- Information regarding submission to the core lab	
Holter monitoring report and ECG strips	Core lab; a report copy is sent to BSC
Reportable Adverse Events, Device Deficiencies, and Protocol Deviations, if applicable	Study site
Data items that do not have an original source document will be collected on a TSF	Study site

Page 67 of 148

## 10.6 Rate Response Substudy (3 Month Visit (90±15 Days Post-implant))

The 3 Month Visit is only for those in the Rate Response Substudy and must be performed as a clinic visit between  $90\pm15$  days after the mCRM Coordinated System is implanted.

A subset of enrolled subjects (up to 59 subjects enrolled earlier in the trial, and preferably sequential enrollments at selected sites) at approximately 15-20 selected study sites with treadmill equipment and facility will complete an assessment of the Rate Response function of the EMPOWER PG. The investigator will review physical capabilities and clinical condition of enrolled subjects, as well as their willingness to perform and complete the Treadmill Walk protocol. This must include an evaluation of any clinical condition that predisposes the subject to higher risk of developing symptoms during the Treadmill Walk. A list of potential risks is described in **Section 18.5**. It is not a deviation if participation is from non-consecutive subjects at the selected Rate Response Substudy site.

Usable datasets from 35 subjects are required to support Secondary Effectiveness Endpoint 2, and it is expected that an enrollment up to 59 subjects will be sufficient to provide the minimum number of datasets required. BSC will notify participating study sites once a sufficient number of datasets are obtained and additional Rate Response testing subjects are no longer needed.

The Rate Response Substudy may consist of some or all of the following:

- Tachometer Functionality Test
- Initial Response Factor Set-up and Selection
- Treadmill Walk
- Hall Walk

Specific information about each of these steps is included in the Rate Response Substudy strategy document (Document 92614291, provided separately).

## 10.6.1 Paced Morphology Sensing Test (PMST)

If the patient is to be programmed to VVIR after testing, consider performing a PMST as described in **Section 10.3.4.6**.

#### 10.6.2 Rate Response Substudy Source Documentation Requirements

Refer to **Table 10-13** for a list source documentation for the Rate Response Substudy and retention requirements.

<sup>28 Note that AF diagnostic episodes labelled "Full S-ECG Report AF" are NOT required.

Page 68 of 148

Data Collection	Retention of Original Source Documentation

 
EMPOWER Programmer Reports:
 
Initial EMPOWER Combined Follow-up Report
 
EMPOWER Real-Time Log Report from PCT (to document loss of capture)
 
Interim Combined Follow-up Report(s) as described in Doc# 92614291 to document sequential programming changes
 
Captured S-ECG Reports from 'Capture All Sense Vectors' on S-ICD programmer for Paced Morphology Sensing Test, if performed
 
Final EMPOWER Combined Follow-up Report
 
	Study site

 
S-ICD Programmer Reports:
 
Initial Summary Report
 
Full S-ECG Report(s) Treated, if applicable
 
Full S-ECG Report(s) Untreated, if applicable
 
Interim Summary Reports as described in Doc
 
92614291 as needed to document sequential programming changes
 
Final Summary Report
 
	Study site
Rate Response Testing: - Rate Response testing data recorded on the TSF including but not limited to handlebar usage and timing of blood pressure measurements - Reports from EMPOWER Programmer, as required, which may include Real-time Log, Combined Follow- up, and Sensor Trending saved on USB following the: - Tachometer Functionality Test - Initial Response Factor Set-up - Treadmill Walk - Hall Walk	Study site: - TSF - Copy of USB files BSC: -USB with associated files
Reportable Adverse Events, Device Deficiencies, and Protocol Deviations, if applicable	Study site
Data items that do not have an original source document will be collected on a TSF	Study site

# Table 10-13: Rate Response Substudy Source Data

<sup>29 Note that AF diagnostic episodes labelled "Full S-ECG Report AF" are NOT required.

## 10.7 6 Month Visit (180 days ± 30 days Post-system Implant)

The 6 Month Visit must be performed as a clinic visit between  $180 \pm 30$  days after the mCRM Coordinated System is implanted.

#### **10.7.1 EMPOWER PG Evaluation**

PCT, Pacing Impedance, and R-wave Amplitude are required to be measured. Collect PCT measurements according to **Section 10.3.1.7**.

It is required to retain the "Real-Time Log Report" from the programmer, documenting at a minimum the LOC portion of the threshold testing (i.e., the lowest voltage setting demonstrating capture and the highest voltage setting that fails to capture). This documentation will be retained at the study site.

If more than one set of electrical measurements are recorded, the final set must be used for the study.

It is required to document the following:

- "%V paced" from the "Combined Follow up Report",
- "Time remaining to EOS" from the "Combined Follow up Report",
- "Charge remaining to EOS" documented on the TSF.

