Primary Effectiveness 1	Communication Success between the S- ICD and EMPOWER PG at 6 Month Visit	95%	88%	One-Sided Lower Pointwise Confidence Limit	2.5%	80%	152 tests/ 38 subjects	30%	220 tests/55 subjects
Primary Effectiveness 2	The percent of subjects with an adequate EMPOWER pacemaker PCT measurement.	95%	80%	One-Sided Lower Confidence Limit	2.5%	90%	57	30%	82

3	Tab	ole of C	Contents						
1.	Тіті	TITLE PAGE1							
2	Pro	ROTOCOL SYNOPSIS6							
3	Тав	LE OF C	ONTENTS						
4	Inte	RODUCTI	ION 21						
•	4.1	Backg	round						
5	Dev	ICE DES	CDIDTION 24						
5	5 1	mCRN	A Coordinated System 24						
	5.1	Imnla	n e oor unateu system						
	53	Non-I	ntable Study Devices 24						
		5.3.1	Non-Implantable Study Devices Associated with the EMPOWER System						
		5.3.2	Model 3870 Programmer Software Application and Associated Firmware25						
		5.3.3	Non-implantable Study Devices Associated with the S-ICD System 26						
	5.4	Access	ories						
	5.5	Additi	onal Equipment27						
6	STU	dy Obje	CCTIVES AND ENDPOINTS27						
	6.1	Study	Objectives						
	6.2	Study	Endpoints						
	6.3	Safety	Endpoints						
	6.4	Effecti	iveness Endpoints						
	6.5	Ancill	ary Objectives						
	6.6	Study	Rationale						
7	STU	DY DESI	GN						
	7.1	Scale a	and Duration						
	7.2	Justifi	cation for the Study Design32						
8	SUB.	JECT SE	LECTION						
	8.1	Study	Population and Eligibility33						
	8.2	Inclus	ion Criteria34						
	8.3	Exclus	sion Criteria35						

9	Subj	ECT AC	COUNTABILITY	36
	9.1	Point o	f Enrollment	36
	9.2	Subjec	t Status and Classification	36
		9.2.1	Intent	36
		9.2.2	Attempt	36
		9.2.3	Partial Implant	36
		9.2.4	Implant	37
	9.3	Access mCRM	to EMPOWER MPS Programmer Software and S-ICD System 1 Programming	ı 37
	9.4	Strateg	gies for Recruitment and Retention	37
	9.5	Withd	rawal	38
	9.6	Lost-to	o-Follow-up	39
	9.7	End-of	-Study Definition	39
	9.8	End of	Study Action Plan	39
10	STUI	ру Метн	HODS	40
	10.1	Data C	Collection	40
	10.2	Enroll	ment Visit	42
		10.2.1	Informed Consent	42
		10.2.2	Enrollment Data	42
		10.2.3	Enrollment Visit Source Documentation Requirements	43
	10.3	Implan	ıt	44
		10.3.1	Implant of the EMPOWER PG	44
		10.3.2	Implant of the S-ICD	48
		10.3.3	S-ICD Firmware Update	50
		10.3.4	mCRM Coordinated System Imaging and Testing	51
		10.3.5	S-ICD Evaluation	56
		10.3.6	S-ICD System Programming Considerations	56
		10.3.7	mCRM Coordinated System Data and Source Documentation Requirements	56
	10.4	Pre-Di	scharge Visit	57
		10.4.1	EMPOWER PG Evaluation	58

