## 10.3.1.7 EMPOWER PG Evaluation

Once the EMPOWER PG is released from the tether, perform the final implant device evaluation, including sensing amplitude, PCT and pacing impedance measurements must be recorded.

It is required that the PCT measurement be collected using the *Temp Brady* programming screen in the following fashion:

- Confirm connection of/ connect the Surface ECG Cable, Model 3153 or equivalent to the subject and the EMPOWER programmer
- Assure that the surface electrogram is displayed on the programmer
- The PCT test(s) shall be conducted at 0.4 ms pulse width
- The starting voltage is discretionary and may be predetermined before documenting the PCT
  - **Note:** it is strongly recommended that the starting voltage to be at least 2 programmable voltage steps above the highest pre-determined loss of capture
- Start the real-time recording on the programmer as the means of documenting the PCT
- Initiate temporary pacing at the desired voltage that consistently captures then stop temporary pacing and step down the voltage by one programmable value (0.1 V or 0.5 V, as appropriate) and restart pacing. Continue in this manner until loss of capture is noted
- Stop the real-time recording
- The threshold is defined as one voltage level above the level where a single Loss of Capture (LOC) is noted.

It is required to retain the "Real-time Log Report" from the programmer, documenting at a minimum the LOC portion of the threshold testing (i.e., the lowest voltage setting demonstrating capture and the highest voltage that fails to capture). This documentation will be retained at the study site.

If more than one set of electrical measurements are recorded, the final set must be used for the study.

**Note:** Additional testing is required once the S-ICD System is implanted and both devices can be tested as a system, as described in **Section 10.3.4**.

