## 10.7.3.2 Communication Test

A single Communication Test is required to be performed at the initial programmed Telemetry Setting in each of the four postures noted in **Figure 10-2**. In the event that multiple communication tests are performed within a posture, only the first Communication Test S-ECG Report obtained at the initial programmed Telemetry Setting will serve as the source document for the endpoint. All required testing should be completed in the selected posture before changing to another posture.

In the event of a communication failure in one or more of the four postures during the single test, perform a Communication Threshold Test (described in **Section 10.3.4.5**) in the posture(s) of communication failure. Use the highest value to program the Telemetry Setting output 1 unit above threshold among all tested posture(s). For example, if the threshold is 5, program the output to 6.

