# 11.1.5.2 Sample Size

A total of 57 measurements (6-month [contact] ms) are required to sufficiently power the Primary Effectiveness Endpoint 2. The following assumptions were used to calculate the sample size:

- Performance goal = 80%
- One-sided significance level = 2.5%
- Power = 90%

The sample size for this study was not determined by this endpoint.

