# 11.1.5.3 Statistical Methods

The analysis for this endpoint will be performed once, either in conjunction with the interim analysis of Safety Endpoint 1, if the analysis of Safety Endpoint 1 is successful in rejecting the null hypothesis, or at the time of the final analysis of Safety Endpoint 1. Two groups of subjects will be included in the endpoint evaluation: (1) PMA Sample cohort subjects with an EMPOWER PG PCT measurement taken at the 6 Month Visit (with a 0.4 ms pulse width), and (2) PMA Sample cohort subjects with a Major EMPOWER MPS System- and Procedure-related Complication between implant and 6 months due to an elevated threshold. The number of responders (PCT at 6 Month Visit  $\leq 2.0$  [contact] ms) divided by the total number of subjects included in the endpoint evaluation will be calculated. The one-sided 2.5% binomial exact lower confidence limit will be calculated and compared to the performance goal of 80%. If the lower confidence limit exceeds 80%, the null hypothesis will be rejected.

To assess the potential impact missing data could have had on the analysis results, a tipping point analysis will be conducted that will include subjects with the EMPOWER PG implanted. The tipping point analysis will assign each subject with missing data as

MODULAR ATP

Page 89 of 148

either being a PCT responder or a PCT non-responder. All possible combinations of these subjects' data will be evaluated along with the actual observed data to find the point, if any, at which the endpoint is failed.

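### The final-set rule for the 6 Month pacing threshold leaves Primary Effectiveness Endpoint 2 open to a device-favouring bias if sites repeat mainly after a failing reading

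*Protocol*

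**What the plan says.** Protocol 10.7.1 requires a PCT at the 6 Month Visit, measured as in 10.3.1.7, and adds: "If more than one set of electrical measurements are recorded, the final set must be used for the study". The same sentence appears in 10.3.1.7, 10.4.1, 10.5.1, 10.8.1 and 10.12.1.

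Protocol 11.1.5.3 builds Primary Effectiveness Endpoint 2 on "subjects with an EMPOWER PG PCT measurement taken at the 6 Month Visit" at 0.4 ms. It adds subjects with a major "Complication between implant and 6 months due to an elevated threshold". The exact one-sided lower limit of the responder proportion is compared with 80%. Under 11.5.1, study success requires this endpoint.

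On the measurement itself, 10.3.1.7 says: "The threshold is defined as one voltage level above the level where a single Loss of Capture (LOC) is noted". The voltage step is 0.1 V or 0.5 V. The starting voltage is left to discretion and may be found before the documented run.

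For Primary Effectiveness Endpoint 1 at the same visit, 10.7.3.2 says that "only the first Communication Test S-ECG Report obtained at the initial programmed Telemetry Setting will serve as the source document for the endpoint". Section 10.3.4.1 has one exception: a repeat may become the official result where intrinsic rhythm may have been absent.

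**The concern.** The tester sees the reading as it is taken, and no masking is described in this single-arm study. No section limits the number of sets, asks why a set was repeated or requires superseded sets to be reported. The only core laboratory (13.4) handles Holter data, and the PCT log stays at the site. The SAP lists PCT only as an ancillary summary and adds no rule on repeats.

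A threshold set by a single lost beat can vary from run to run. A reading just above 2.0 gives a reason to repeat, and a reading below it does not. If repeats follow that pattern, the last set is a selected value and the selection favours the device. A permitted repeat is not a deviation, so monitoring would not correct it. The tipping-point analysis in 11.1.5.3 covers missing data only and would not show it.

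A last-set rule has a clear purpose at implant, where the device may be repositioned (10.3.1.6). That reason does not apply at 6 months, and the protocol does not explain why its two primary effectiveness endpoints are handled in opposite ways.

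**Working it through.** **The plan's own figure.** Inputs: goal 80%, one-sided 2.5% and power 90% (Protocol 11.1.5.2); expected rate 95% (Synopsis table). The normal approximation gives

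n = [(1.960·√(0.80·0.20) + 1.282·√(0.95·0.05)) / 0.15]² = 50.2.

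The continuity correction, n/4·(1 + √(1 + 2/(n·0.15)))², gives 56.7, so 57. With 30% attrition, 57/0.70 = 81.4, so 82. Both match the plan, so there is no sample-size error here.

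**Pass rule.** The exact lower 97.5% limit exceeds 80% at 52/57, 117/134 or 191/223 responders. At a true rate of exactly 80% the chance of passing is 1.86%, 1.83% and 1.85%. The endpoint is analysed alongside Safety Endpoint 1, at 134 or 223 subjects followed for 6 months. The number with an evaluable PCT is not stated, so I use 134.

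**How many conversions matter.** If a fraction f of failing readings ends as a pass, the observed rate is 0.80 + 0.20·f. At n=134 the chance of passing exceeds 2.5% once f passes 2.3%, which is 0.023 × 26.8 = 0.6 subject on average. At f = 10% it is 6.4%.

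**Model for repeats (all inputs assumed).** True PCT T is lognormal with median 1.2 and log SD 0.6, so 80.3% of subjects lie at or below 2.0 (taken as volts). Each reading has normal error with SD s. A share r of readings above 2.0 is repeated once, and the repeat counts.

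- P(one reading passes, given T) = Φ((2 − T)/s) = p(T)
- First-reading rate = E[p(T)]
- Rate under the final-set rule = E[p(T)] + r·E[(1 − p(T))·p(T)]

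Numerical integration gives the responder rate, with the chance of at least 117/134 in brackets:

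| s (V) | first reading only | r = 25% | r = 50% | r = 100% |
|---|---|---|---|---|
| 0.1 | 80.13% (2.0%) | 80.46% (2.5%) | 80.79% (3.1%) | 81.44% (4.6%) |
| 0.2 | 79.71% (1.5%) | 80.38% (2.4%) | 81.04% (3.6%) | 82.38% (7.9%) |
| 0.3 | 78.99% (0.9%) | 80.02% (1.9%) | 81.05% (3.6%) | 83.11% (11.6%) |

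Simulating the same model gives 0.9 to 2.1%, 2.0 to 2.7%, 3.3 to 3.8% and 4.9 to 12% for the four columns. The two methods agree within 0.4 percentage points, and the conclusion does not depend on which is used.

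**At the planned rate.** With a true rate of 95%, the chance of passing at n=134 is above 99.9% with or without repeats.

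**The case against.** The strongest reply is that this is a pre-specified rule and not best-of-n. The final set counts whichever way it falls, so a repeat can turn a pass into a fail. That stands. A reader might infer that the rule can only raise the responder rate, or that sites will use it to rescue failures. The documents support neither. The rate rises only if repeats are concentrated after failing readings, and nothing in the plan says how often or why sites repeat.

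A reader might also infer that sponsor staff could run the test as they wish. Section 16.6 allows them to operate equipment only at the investigator's request and under supervision, and bars them from independently collecting primary or secondary endpoint data.

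Other safeguards are real:

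- The run is recorded in real time, and both the lowest capturing and the highest non-capturing voltage must be documented.
- Monitors have direct access to source documents (Section 17).
- A single lost beat is a strict criterion.
- Elevated-threshold major complications enter the denominator separately, so exposure lies mainly near 2.0.

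These deter misuse, but they do not stop a legitimate repeat from replacing a failing value.

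The contrast with Endpoint 1 is also softer than it looks. That test is pass/fail at one setting, threshold testing follows a failure, and 10.3.4.1 allows a technical repeat. The contrast still shows that the protocol already has a workable first-test rule.

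Finally, a first-set rule alone would leave open the undocumented pre-run in 10.3.1.7. That is correct, so the fix has to cover it.

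**Conclusion.** The point holds as a conditional bias route, not as a demonstrated bias. The final-set rule is neutral in itself and favours the device if sites repeat mainly after a reading above 2.0.

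With a true rate near the goal, retest SD 0.1 to 0.3 V, one repeat and n=134, the chance of passing is about 2.0 to 2.7% when a quarter of failing readings are repeated, which is close to the nominal 2.5%. It is 3.3 to 3.8% at one half and 4.9 to 12% if all are repeated, against 0.9 to 2.1% on first readings only. If the true rate is near the planned 95%, the effect is negligible.

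The repeat frequency, retest SD and PCT distribution are assumptions, because the documents give none. The change is worth making because it is cheap and protects the test when performance is near the goal, which is the case the test must control.

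**What to change.** In Protocol 10.7.1 and 11.1.5.3:

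- Define the endpoint value as the first technically valid documented PCT set at 0.4 ms at the 6 Month Visit.
- Let a repeat replace it only for a technical failure documented before the repeat, such as a missing surface ECG or a wrong pulse width.
- Record every set taken at that visit, including any pre-run used to choose the starting voltage under 10.3.1.7.
- Report the final-set result as a sensitivity analysis.

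This governs only which reading is analysed, not device programming. The final-set rule can stay at implant.

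The cost is a short text change in each section and added entries on the existing Technical Source Form. No extra testing is needed, and the sample size of 57 (82 with attrition) and the pass rule are unchanged. The downside is that the responder rate may come out slightly lower, because a single noisy reading can understate the true rate. In the model above, first readings give 79.0 to 80.1% against a true 80.3%.
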